##### **Analytic approach:**

For DAPPER, the outcomes will be improvement in pain, depressive symptoms, and communication with health care providers. A database will be created and stored on a password protected encrypted computer. Prior to conducting the analysis, the distribution of the data will be examined to determine if they meet the assumptions of the analytical model and to explore the pattern of missing data. The number of sessions attended will be computed as an indicator of acceptability. To test the effect of the intervention on outcomes (depressive symptoms, pain), generalized estimating equations will be used (GEE) with time, group, and the time x group interaction. We will not be sufficiently powered to detect a significant effect; interpretation of the results will be based on the effect size associated with the time by group interaction for each outcome. One advantage of GEE is it allows all participants' data to be included in the analysis, even those who do not complete the study, providing an intention-to-treat analysis. We will also conduct sensitivity analyses with completers only and compare the effect size to the ITT analysis to estimate the effect size when all participants adhere to the intervention.

Acceptability of the intervention will be examined in multiple ways. We will examine percentages of people who stayed in each arm of the study and conduct numerous descriptive correlational analyses of the

association between the intervention compliance and other variables. These analyses will quantify intervention implementation by demographic and participant health variables. Analyses that utilize the post-randomization data (e.g. treatment compliance) will be evaluated in supplementary analyses. We will distinguish non-compliance with intervention from attrition or loss to follow-up, i.e. missing data. We will also use the one-on-one qualitative interviews to examine acceptability of the intervention.

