### **1. Abstract**

Older African American women experience disproportionate rates of chronic conditions in comparison to other groups. Pain, depressive symptoms, and frailty often co-occur in African American women aging with chronic conditions and this combination can lead to disability and poor quality of life. Addressing pain and depressive symptoms may improve or delay the progression to frailty. To our knowledge there is little work being done in this population to address both pain and depression. The Depression and Pain Perseverance through Empowered Recovery (DAPPER) program is person directed and will consist of 8 nurse visits during which the nurse assesses each participant for pain, depression, and frailty, then implements a manualized individually tailored intervention. The data collection visits, and nurse visits will take virtually. We propose a pilot trial that is a wait list randomized control pilot to test the acceptability and obtain a preliminary effect size for the intervention. We will recruit 64 ( $\geq$ age 50) African American women who report pain intensity of 3 or higher that interferes with their activities, depressive symptoms lasting more than two weeks, are pre frail or frail, and live in the community/are not institutionalized. The sample will be recruited through the PI's previous study, community recruitment flyers distributed virtually, and word of mouth campaigns. Participants will be randomized into either the intervention or the wait list control group. Once the intervention group has completed their visits, the wait list control group will begin their visits. All participants will be offered the same information and format of nurse visits. The nurses will systematically tailor the content of the visits to the participants' risk profile and goals based on protocols. All participants will be assessed at the start of the study, at 12 weeks, and 24 weeks. The primary outcomes will be pain, depressive symptoms, and frailty status. Other endpoints include goal attainment, stress (cytokines), self-report, self-efficacy, and communication with health care providers. We will also examine the acceptability of the intervention using intervention compliance and one-on-one qualitative interviews. This study will offer either virtual or in person visits based on the preference of the participants.

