### **2. Objectives**

The aims of this pilot project are to 1) test the Depression and Pain Perseverance through Empowered Recovery (DAPPER) program for feasibility and acceptability. Specifically, we will 1) test the effect size of DAPPER on pain and depressive symptoms from baseline to 12 weeks (compare intervention to wait list control group) and then at 24 weeks to compare the intervention group to wait list control group once again, 2) estimate preliminary effect sizes for DAPPER in reduction of frailty, and 3) measure effect sizes and feasibility of measuring cytokines.

This study is being supported through funding from the Harold Amos Medical Faculty Program and the Johns Hopkins Older Adults Independence Pepper Center.

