### Approach

**4.a Theoretical Framework:** Self-regulation theory is the theoretical framework for this study. Self-regulation theory involves two tenets: 1) participants manage their response based on their experiences (experiences with pain, depression, and frailty treatments) and knowledge of an event and 2) participants' goals are to maintain comfort and decrease the negative effects of an illness (pain depression and/or frailty) on their lives. The intervention is participant centered and participant driven. This means that the participants' experiences and existing knowledge about pain, depressive symptoms, and frailty will drive the goals that they set. For example, a participant may have experienced pain, depression symptoms, and frailty; she is no longer able to go work in her garden. Her goal may be to be able to garden again. This would provide comfort, decrease the effects of these three conditions, and potentially improve her symptoms.

**Design overview of the study:** The design of the study is outlined in the above figure. The outcomes will determine effect sizes on the intervention's effect on pain and depressive symptoms. Outcomes will be measured at 12 weeks (compare intervention and wait list control group) and at 24 weeks (look at outcomes for wait list control group and outcomes over time for intervention group). Goal attainment will be measured at 12 weeks and 24 weeks. At 24 weeks, we will also conduct virtual semi-structured one on one individual interviews with participants to determine feasibility and acceptability.

The intervention group (n=30) will start the study and will receive eight nurse visits that will be focused on decreasing pain, depressive symptoms, and meeting participant selected goals set in these areas. The wait list control group will receive monthly calls by a study team member to ensure their contact information

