#### **5. Study Statistics**

##### **Sample size calculation and analysis of aims**

**Sample size:** To calculate effect sizes for planning a definitive trial our sample size calculations were based on the need to pilot DAPPER for pain and depressive symptoms. We assume an attrition rate of 13% during the 16-week follow-up based on the CAPABLE trial. Based on these assumptions, an initial sample size of 64 participants (32 in the intervention group and 32 in wait list control) would yield 52 participants (25 intervention, 25 wait list control) after attrition. It is unlikely we will detect a significant difference between the groups due to small sample size and limited follow-up.

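### The planned GEE neither adjusts for baseline nor constrains the arms to a common baseline mean, so its 12-week interaction is a change-score contrast: unbiased, but less precise than a baseline-adjusted one

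*Combined protocol and SAP*

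**What the plan says.** Section 5 (Study Statistics, Analytic approach) gives the model for depressive symptoms and pain: "generalized estimating equations will be used (GEE) with time, group, and the time x group interaction". It then says that "interpretation of the results will be based on the effect size associated with the time by group interaction for each outcome". No baseline covariate is listed, and no constraint that the arms share a baseline mean. The working correlation and the coding of time (categories or a linear trend) are not stated either.

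The Abstract sets the schedule: "All participants will be assessed at the start of the study, at 12 weeks, and 24 weeks". Section 2 (Objectives) states the aim as to "test the effect size of DAPPER on pain and depressive symptoms from baseline to 12 weeks", comparing the intervention group with the wait list. The randomisation steps in the DAPPER Protocol section place allocation after the baseline interview, within 48 hours of it. The PHQ9 and pain questionnaires are therefore completed before allocation.

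The sample size paragraph gives the purpose of the numbers as obtaining effect sizes to plan a definitive trial. The plan says openly that it lacks power to detect a difference.

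**The concern.** The plan does not say in so many words that baseline is a level of time. It is, however, the only reading under which the interaction estimates an effect from baseline to 12 weeks. On that reading, baseline is one of the repeated outcomes and each arm has its own free baseline mean. The 12-week interaction is then a difference in mean change.

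Randomisation makes the true baseline means equal, and this model does not use that fact. A change score subtracts the whole of a chance baseline imbalance, whereas regression on baseline subtracts only the part that predicts the follow-up value. At stake is the width of the interval around the effect size, which is what the plan says it will interpret and carry forward.

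**Working it through.** **1. The plan's own numbers.** The inputs are "an initial sample size of 64 participants (32 in the intervention group and 32 in wait list control" and "We assume an attrition rate of 13% during the 16-week follow-up based on the CAPABLE trial". The stated result is "would yield 52 participants (25 intervention, 25 wait list control) after attrition".
- 64 × 0.87 = 55.7, or 32 × 0.87 = 27.8 per arm. This is neither 52 nor 50, and 25 + 25 = 50, not 52.
- A start of 60 gives 60 × 0.87 = 52.2, and the Approach section has "The intervention group (n=30) will start the study".

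The stated figure is not reproduced. I use 25 per arm because the plan states it. The percentages in step 3 do not depend on it. At 28 per arm and rho 0.5, the half-width would go from 0.52 to 0.45 SD.

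**2. What the interaction estimates.** I simulated one complete data set with three visits, 25 women per arm and categorical time. The 12-week interaction was 0.3569 from GEE with independence, 0.3569 from GEE with exchangeable correlation, and 0.3569 as the hand-computed difference in mean change.

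**3. Precision with equal SDs and complete pairs.** Rho and the SD are assumptions, since the documents give neither. The SD is set to 1 and n is the number per arm.
- Change contrast: variance = 4(1 − rho)/n
- Baseline-adjusted contrast: variance = 2(1 − rho²)/n
- Ratio = (1 + rho)/2, so the share given up is (1 − rho)/2

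| rho | variance given up | 95% half-width, change | 95% half-width, adjusted |
|---|---|---|---|
| 0.3 | 35% | 0.66 SD | 0.53 SD |
| 0.5 | 25% | 0.55 SD | 0.48 SD |
| 0.7 | 15% | 0.43 SD | 0.40 SD |
| 0.8 | 10% | 0.35 SD | 0.33 SD |

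At rho 0.5 the standard errors are √(4 × 0.5/25) = 0.283 and √(2 × 0.75/25) = 0.245. The half-width is therefore about 13% smaller. The change contrast would need 25/0.75 = 33 per arm to match.

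**4. Cost of estimating the slope.** In 20,000 simulated trials at 25 per arm, the variance saved was 33%, 24% and 13% at rho 0.3, 0.5 and 0.7.

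**5. Dropout.** With 32 baselines and 25 follow-ups per arm, GEE on all available data is no longer exactly the complete-pair change contrast. I compared it with a model that has a common baseline mean and the correct correlation. At rho 0.3, 0.5, 0.7 and 0.8 the loss is:
- exchangeable working correlation: 30%, 21%, 12% and 8%
- independence: 31%, 25%, 26% and 32%

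At rho 0.5, for example, the variances are 0.0600 (constrained), 0.0756 (exchangeable) and 0.0800 (independence).

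**6. Unequal SDs and the entry thresholds.** In general the share given up is (SD_baseline − rho × SD_follow-up)² / Var(change). This is never negative, but it shrinks when the baseline SD is the smaller one. With follow-up SD 1.2 times baseline and rho 0.5, it is (1 − 0.6)²/(1 + 1.44 − 1.2) = 0.16/1.24 = 13%.

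Eligibility requires PHQ9 of at least 5, including at the baseline visit, and pain of at least 3. Assume normal scores with rho 0.5 before selection. Selection on baseline leaves the slope (0.5) and residual variance (0.75) unchanged.
- Upper 84% kept: baseline SD 0.79, and 0.25 × 0.79² = 0.156. Loss = 0.156/(0.156 + 0.75) = 17%.
- Upper 69% kept: loss 14%.
- Upper 50% kept: baseline SD 0.60, and 0.25 × 0.60² = 0.09. Loss = 0.09/0.84 = 11%.

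**The case against.** The case for leaving the model alone is reasonable. Both estimators target the same effect under randomisation, so this is a matter of efficiency and not an error. The trial is a pilot whose overall aim is feasibility and acceptability, it disclaims power twice, and no hypothesis decision turns on this interval. On the scale a reader sees, the gain at rho 0.5 is a half-width about 13% narrower. All of that stands. It limits the weight of the point without removing it, because the plan rests its interpretation on the effect size.

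Four stronger readings are tempting, and the documents do not support them.
- **A fixed loss of a quarter.** A reader might infer this, but it needs rho = 0.5 and equal SDs, and the documents give neither.
- **Thresholds make it worse.** Selection does lower the observed rho. In step 6 it falls from 0.50 to 0.42, 0.37 and 0.33, and (1 − rho)/2 would then suggest 29%, 31% and 34%. That formula assumes equal SDs, which selection breaks. The actual losses are 17%, 14% and 11%.
- **Every outcome can be adjusted.** Goal attainment is first rated at nurse visit five and has no baseline. Saliva is collected over the two days after the first data visit, so collection before allocation is not assured, and women outside Maryland give none.
- **Adjustment has no downside.** It costs one estimated slope. A simple covariate model also drops women with no follow-up, whom the plan chose GEE to keep.

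**Conclusion.** The point holds as a modest, nearly free gain in precision. As written, the model yields a change-score contrast at 12 weeks that is unbiased and, in large samples, never more precise than the baseline-adjusted one. With equal SDs the variance given up runs from 35% at rho 0.3 to 10% at rho 0.8. For PHQ9 and pain intensity it is likely to be lower, since entry thresholds narrow the baseline spread. An illustrative range is 11% to 17% for a correlation of 0.5 before selection.

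These figures rest on assumed correlations and, in step 6, on normal scores. Under dropout they also depend on the unstated working correlation. The direct equality with mean change assumes categorical time. If time is linear, the interaction is a slope difference that draws in week 24 as well.

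**What to change.** For pain and depressive symptoms, name the 12-week group difference as the contrast and estimate it in one of two ways:
- with that outcome's baseline value as a covariate; or
- with a constrained longitudinal model that has categorical time, a common baseline mean for both arms and unstructured within-person correlation. This also keeps women who have only a baseline value.

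The second option must not be fitted with an independence working correlation. With complete data it would then collapse to the raw 12-week difference, with variance 2/25 = 0.080. The planned change contrast has 4 × 0.3/25 = 0.048 at rho 0.7, so the result could be worse than the current plan.

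Report the adjusted difference in raw units with its 95% confidence interval, and state which SD standardises it. The baseline SD should not be the only one used, because it is restricted by the thresholds. In the illustration above it is 0.79 to 0.60, against a follow-up SD of 0.95 to 0.92. The standardised effect would then be about 20% (0.95/0.79) to 50% (0.92/0.60) larger than on the follow-up SD, which matters when planning the next trial.

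The cost is one estimated slope and one sentence in the analysis section. No new data are needed.

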**Acceptability Qualitative Interviews:** Upon completion of the intervention, the follow up interviews will be scheduled with 10 randomly selected participants from both the intervention and wait list control groups. These interviews will be done by a study team member. The interviews will be scheduled and completed with participants via phone or video. We will ask their thoughts on the intervention and ask for what worked and what did not. The interviews will be audio recorded with a digital recorder only. We will make sure that all information is in a locked file cabinet at Johns Hopkins School of Nursing. We will keep all audio recordings separate from documented person information. We will ask participants to avoid using names in the interviews. The audio recordings will be stored on an encrypted computer after the interviews are completed. The PI will review all transcripts and work with study team to identify themes surrounding intervention changes and conduct intervention mapping to refine the intervention for the next grant application. The audio recordings will be stored on an encrypted computer after the interviews are

completed. Production transcripts will transcribe the follow up interviews. The PI will review all transcripts and work with study team to identify themes surrounding intervention changes and conduct intervention mapping to refine the intervention for the next grant application.

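### The plan does not say which time-by-group term gives the planning effect size, and its 24-week between-arm comparison may come after the wait-list arm has had DAPPER

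*Combined protocol and SAP*

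**What the plan says.** The Abstract sets assessments at the start of the study, at week 12 and at week 24. The other relevant statements are these.

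- **Objectives, first aim.** For the first follow-up, the plan will "test the effect size of DAPPER on pain and depressive symptoms from baseline to 12 weeks (compare intervention to wait list control group". For the second follow-up, the same aim adds a further between-arm look, worded "then at 24 weeks to compare the intervention group to wait list control group once again".
- **Approach, design overview.** The first follow-up is described in the same way: "Outcomes will be measured at 12 weeks (compare intervention and wait list control group". The second is described differently, arm by arm: "at 24 weeks (look at outcomes for wait list control group and outcomes over time for intervention group".
- **Wait-list start, Abstract.** "Once the intervention group has completed their visits, the wait list control group will begin their visits".
- **Wait-list start, DAPPER Protocol section.** The wait-list arm is held back until the intervention group has finished the study, not just its visits.
- **Analytic approach.** A GEE with time, group and their interaction is fitted to depressive symptoms and pain. The plan accepts that it lacks power for significance, and so "interpretation of the results will be based on the effect size associated with the time by group interaction for each outcome". The coding of time is not given.
- **Sample size.** The effect sizes are wanted for designing a later definitive trial.
- **Interviews.** The design overview says: "At 24 weeks, we will also conduct virtual semi-structured one on one individual interviews with participants to determine feasibility and acceptability". The Acceptability Qualitative Interviews paragraph draws its sample from the two arms: "Upon completion of the intervention, the follow up interviews will be scheduled with 10 randomly selected participants from both the intervention and wait list".

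**The concern.** With significance testing set aside, the interaction effect size is the main quantitative result of the pilot and an input to the next trial. Two things leave it open.

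First, the plan does not say which term it is. Two analysts could follow the Analytic approach faithfully and carry different numbers forward.

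Second, the Objectives invite a between-arm effect size at week 24, and the plan does not settle whether the wait-list arm is still untreated then. If that arm has begun or finished DAPPER, the contrast compares earlier with later treatment. An effect size diluted in this way could lead to an oversized definitive trial, or to none.

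**Working it through.** **No figure of the plan's own to reproduce.** The documents give no target effect, SD or within-person correlation for this analysis. Effect sizes and correlations below are assumptions.

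**Step 1: the two start rules.**
- If the DAPPER Protocol wording is literal, finishing the study includes the 24-week assessment, so the wait-list arm is untreated at week 24. The plan then lists no later assessment to capture that arm's response to DAPPER.
- If finishing the study loosely means finishing the visits, or the visits plus a post-intervention assessment, the two rules agree. The wait-list arm can then have received DAPPER before week 24.
- The interview statements fit the earlier start, but only if both describe the same interviews. The Acceptability paragraph gives no week.

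**Step 2: the 24-week contrast.** Let d be the effect of DAPPER, kept in full by the intervention arm, and f the share of d that the wait-list arm has gained by week 24. The contrast is d - f x d = d(1 - f). With d = 0.40 SD:

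| f | 24-week contrast (SD) |
|---|---|
| 0 | 0.40 x 1 = 0.40 |
| 0.5 | 0.40 x 0.5 = 0.20 |
| 1 | 0.40 x 0 = 0 |

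**Step 3: the interaction terms.** Let D0, D12 and D24 be the group differences at the three assessments, with D0 = 0 by randomisation.
- Categorical time gives two terms, D12 and D24.
- Linear time gives one slope. The centred times are -12, 0 and 12, and their squares sum to 288. The weights are -12/288 = -1/24, 0 and 12/288 = 1/24. The slope is therefore D24/24 per week, which is D24 over 24 weeks. With complete data, week 12 has zero weight.

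**Step 4: check by simulation.** An exchangeable GEE was fitted to 20,000 simulated participants per arm with complete data, an assumed 0.5 SD benefit, an untreated wait list at week 12 and a fully treated one at week 24. In absolute value, the categorical terms were 0.50 at week 12 and 0.02 at week 24. The linear term was 0.0007 per week, or 0.0007 x 24 = about 0.02 over 24 weeks. The same data thus give about half an SD or almost nothing, depending on the term reported.

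**Step 5: precision of a week-12 estimate.** Take the plan's 25 per arm after attrition and an assumed baseline-to-week-12 correlation of 0.5.
- Change score: 1.96 x sqrt(2 x 2(1 - 0.5)/25) = 1.96 x sqrt(0.08) = 0.55 SD.
- Baseline-adjusted: 1.96 x sqrt(2 x (1 - 0.25)/25) = 1.96 x sqrt(0.06) = 0.48 SD.
- The variance ratio is (1 + 0.5)/2 = 0.75.

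**The case against.** The strongest defence is that the plan describes an ordinary wait-list sequence: intervention, 12-week assessment, crossover, 24-week assessment. The DAPPER Protocol section schedules a final data visit when the nurse visits end, so finishing the study may mean no more than that. The two start rules then agree, and the 24-week sentence in the design overview makes sense. The residue would be one loose clause in the Objectives, which might even mean immediate versus delayed treatment. This reading is plausible. But it is the one under which the wait-list arm can be treated before week 24, so the clause in the Objectives cannot stand as an effect size for DAPPER against no DAPPER.

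It is also fair to say that the design overview does not call its 24-week look within-arm or rule out a comparison, and that no section proposes linear time. Linear time is only not excluded.

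A reader might infer more than the documents support:

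- **That week 24 is certainly contaminated.** The literal DAPPER Protocol rule would prevent it.
- **That week 12 is contaminated as well.** This would need assumptions about visit spacing and about a start rule for each participant that the visible text does not give. The design figure is not shown and may settle the timing, so nothing can be said about spacing being absent from the plan.
- **That a between-arm cytokine estimate is biased.** The Objectives ask for cytokine effect sizes and feasibility, but no section specifies a between-arm cytokine analysis.

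Finally, the half-width of 0.48 SD exceeds the illustrative effect of 0.40 SD, so this pilot could not tell the scenarios in the table apart. That limits how finely they should be read. It does not justify carrying forward a term that may be biased towards zero.

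**Conclusion.** The point holds in conditional form and should be fixed before analysis. The Objectives and the design overview differ on week 24, and the Abstract and the DAPPER Protocol section agree on the wait-list start only if finishing the study is read loosely.

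Under that loose reading, the 24-week contrast is d(1 - f). It falls from the full effect to zero as the wait-list arm's gain rises from none to all, and a linear slope inherits the same loss. This assumes that the intervention arm keeps its gain; d and f are illustrative. Under the literal reading week 24 is not diluted, but the Analytic approach still does not name the interaction term that supplies the planning effect size. Text therefore has to change on either reading.

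**What to change.** 1. **Reconcile the timing.** Make the Abstract, Objectives, design overview and DAPPER Protocol section agree on when wait-list visits begin relative to the 12- and 24-week assessments.
2. **Name the estimate.** In the Analytic approach, treat time as categorical. Define the planning effect size as the group contrast at week 12, which the Objectives and the design overview both name. Adjust it for the baseline value already collected and give a 95% CI. Report the sessions each arm had received by then, so that a reader can see what was compared; sessions attended are already to be computed. The adjustment is a secondary gain in precision.
3. **Limit week 24.** Unless the reconciled text shows the wait-list arm untreated at week 24, take the 24-week between-arm comparison out of the effect-size aim or relabel it as immediate versus delayed DAPPER. Report week 24 by arm, as in the design overview.

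The cost is wording in four sections, with no new data or participants. The downside is that no controlled 24-week effect can be claimed if crossover comes first. The week-12 estimate also stays imprecise, at about plus or minus 0.48 SD under the assumptions above.

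### Including dropouts' data in GEE does not by itself secure an intention-to-treat effect size, and the gap from the completers-only result is not an adherence effect

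*Combined protocol and SAP*

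**What the plan says.** Section 5, Analytic approach, sets out the model for pain and depressive symptoms: "generalized estimating equations will be used (GEE) with time, group, and the time x group interaction". Because the trial is not powered for significance, "interpretation of the results will be based on the effect size associated with the time by group interaction for each outcome". The plan then lists as an advantage of GEE that everyone's data enter the analysis, "even those who do not complete the study, providing an intention-to-treat analysis".

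The sensitivity analysis follows: "We will also conduct sensitivity analyses with completers only and compare the effect size to the ITT analysis". Its declared purpose is to estimate the effect size if every participant adhered.

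On attrition, the sample size paragraph says "We assume an attrition rate of 13% during the 16-week follow-up based on the CAPABLE trial". It gives no rate by arm and none for 24 weeks.

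The plan names no working correlation, missing-data assumption, weighting or imputation. It does say that the pattern of missing data will be explored, that retention will be examined in each arm, and that non-compliance will be kept separate from loss to follow-up.

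**The concern.** Intention-to-treat requires a comparison of all women as randomised at follow-up. Putting a dropout's baseline value into the model does not supply her follow-up value. With an independence working correlation, the interaction compares the baseline mean of everyone with the follow-up mean of those who stayed. If those who stayed differ from those randomised, and differ in another way in the other arm, the contrast absorbs that difference.

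The arms carry different burdens: eight nurse visits against monthly contact calls. Dropout that works differently by arm is therefore plausible, although the documents neither assume it nor give data on it.

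The estimated effect sizes are meant for planning a definitive trial, so a bias would pass straight into that trial's assumptions. The completers-only comparison adds a second risk: a gap produced by who stayed would be reported as the benefit of adherence.

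**Working it through.** **The plan's own figure.** The only stated number bearing on this point is the retained sample: "would yield 52 participants (25 intervention, 25 wait list control) after attrition". From 64 at 13% attrition, 64 × 0.87 = 55.68, which is neither 52 nor 25 + 25 = 50. Read backwards, 52 of 64 implies 1 − 52/64 = 18.8% attrition, and 50 of 64 implies 21.9%. This inconsistency is a separate matter. It explains why the check below uses both 13% and 22%, with 30% as an upper value.

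**Inputs.** From the documents: GEE with time, group and their interaction; 13% attrition; 32 per arm. Assumed, because the documents do not give them: SD 1; true 12-week effect −0.40 SD (lower scores are better); within-person correlation ρ of 0.3, 0.5 or 0.7; dropout in the intervention arm rising with baseline severity by 1 log-odds unit per SD; dropout in the control arm unrelated to severity.

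**Formulas.** Let X be standard normal baseline severity and q(X) = 1/(1 + exp(−(a + X))) the dropout probability, with a chosen so that the mean of q equals the dropout rate p. Intervention-arm completers then have a mean baseline lower than that of all women randomised to that arm by

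d = E[X·q(X)] / (1 − p).

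Their mean at follow-up is lower by ρ·d. Hence:

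- Independence GEE (follow-up of stayers minus baseline of all): bias = −ρ·d.
- Completers-only change (both means from stayers): bias = −ρ·d + d = +(1 − ρ)·d.
- Gap between the two: (1 − ρ)·d + ρ·d = d, whatever the correlation or the true effect.

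**Results (bias in SD, ρ = 0.3 / 0.5 / 0.7).**

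| Dropout p | a | d | Independence GEE | Completers only |
|---|---|---|---|---|
| 13% | −2.235 | 0.116 | −0.035 / −0.058 / −0.081 | +0.081 / +0.058 / +0.035 |
| 22% | −1.510 | 0.189 | −0.057 / −0.095 / −0.133 | +0.133 / +0.095 / +0.057 |
| 30% | −1.018 | 0.253 | −0.076 / −0.126 / −0.177 | +0.177 / +0.126 / +0.076 |

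Independence GEE therefore estimates between −0.40 − 0.035 = −0.44 and −0.40 − 0.177 = −0.58. Completers only estimates between −0.40 + 0.177 = −0.22 and −0.40 + 0.035 = −0.37. As a share of 0.40, the GEE bias runs from 0.035/0.40 = 9% to 0.177/0.40 = 44% (45% if 0.177 is first rounded to 0.18). At 13% dropout and ρ = 0.5 it is 0.058/0.40 = 14%.

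**Trial-sized check.** In 400 simulated trials of 32 per arm (ρ = 0.5, 22% dropout), independence GEE averaged −0.51, completers-only change −0.30, exchangeable GEE −0.40 and baseline-adjusted analysis −0.41. The formulas give −0.495 and −0.305 for the first two. With a standard error of about 0.28 SD per trial, the simulation error is about 0.28/√400 = 0.014, so the two agree.

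**When the bias disappears or shrinks.** If dropout depends on severity in the same way in both arms, the terms cancel and both estimates return −0.40. In a wider set of two-visit scenarios (true effect 0.3 or 0.5 SD, dropout 13% or 22%, log-odds slope 1 or 2), dropout depending on observed values gave:

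- Same in both arms, independence: −2% to +1%.
- One arm only: +11% to +65% with independence, 0% to +3% with exchangeable.
- Opposite directions in the two arms: +24% to +130% with independence, 0% to +18% with exchangeable.

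**The case against.** Several points on the other side stand.

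- The plan does not call the GEE estimate valid or unbiased. Its statement can be read as describing which women are analysed. But the result is labelled as intention-to-treat and then used as the benchmark for the completers analysis, so the label carries weight.
- A reader might infer that any severity-related dropout biases the interaction. It does not: the dropout must act differently by arm, and the documents contain no evidence that it will.
- A reader might also take a bias of about a quarter as the expected result. That figure belongs to one combination: independence, one-arm dependence, 22% dropout, correlation 0.5 and effect 0.40. The effect, correlation and dropout mechanism are not in the documents, no working correlation is chosen, and 22% comes from the inconsistent 25 + 25 rather than from a planned rate.
- Sampling error is larger in most scenarios. With 25 per arm and correlation 0.5, the 95% half-width is 1.96 × √(2/25) = 0.55 SD. The plan disclaims power, and feasibility and acceptability are aims in their own right. This limits the consequence, but it does not excuse a systematic error that can be avoided.
- Exploring missingness and retention by arm could reveal differential dropout. Neither step leads to a stated change of analysis.

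The adherence reading has no comparable defence. Even with exchangeable GEE, nearly unbiased in the one-arm scenarios, the completers-only bias of (1 − ρ)·d remains. A woman can complete the assessments and skip sessions, and the same section promises to keep non-compliance and attrition apart.

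**Conclusion.** The concern holds in a conditional form. Using all available data in GEE does not by itself protect the intention-to-treat contrast, and the plan leaves open the working correlation that largely decides whether the bias is near zero or material. With independence and severity-related dropout in the intervention arm only, the bias is about 0.04 to 0.18 SD on an assumed effect of 0.40 SD, and about 14% at the stated attrition with correlation 0.5. In those scenarios the completers-only result errs in the opposite direction, so the gap measures selection rather than adherence.

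The documents do not support saying that the trial's effect size will be biased, that one percentage describes the bias, or that GEE must be abandoned. The sizes rest on the assumed effect, correlation and dropout mechanism. The direction would reverse if less severe women were the ones leaving the intervention arm.

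**What to change.** Make the primary analysis one that is valid when dropout depends on observed values. Options are a likelihood-based mixed model for baseline, 12 and 24 weeks with unstructured covariance, including all randomised women, or GEE combined with weighting or multiple imputation. At minimum, if plain GEE is kept, specify a working correlation other than independence and a small-sample variance correction.

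In either case, state the missing-data assumption, delete the statement that GEE by itself provides intention-to-treat, and stop presenting the completers-only result as the effect under full adherence. It can remain as a descriptive comparison.

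The cost is wording in Section 5 and a little more analysis work. No new data are needed and standard software suffices. The mixed model assumes approximately normal scores. None of these options protects against dropout that depends on unobserved values: in the scenarios examined, such dropout in one arm left a bias of 12% to 48% even with an exchangeable working correlation. The stated assumption should acknowledge this.
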